### 3.1.2 Study Treatment Phase

Following adolescent consent, subject information (name and smart phone number) will be sent to the intervention delivery platform, called the Way to Health (WTH) platform, using secure, HIPAA-compliant methods for the transmission of protected health information.

The WTH platform will help with management of the financial incentive interventions.

Adolescent subjects will enroll in the smoking cessation program – the Quitline. Adolescents will continue in the program for 10 weeks, depending upon their individual needs. See Section 7 description for full details on Quitline delivered treatment.

### 3.1.3 Follow-up Phase

To be eligible for the follow-up phase, adolescents must self-report tobacco cessation. All study subjects will be contacted by the study team 10 weeks after study enrollment to inquire about smoking cessation (defined as no tobacco use in the last 30 days). For subjects that report quitting, to confirm cessation, subjects will complete a salivary cotinine specimen. The result will either be collected at the clinic or collected remotely, in the latter case performed in front of a live video-conference with a study staff member to confirm adherence. The result can be reported immediately.

## 3.2 Allocation to Treatment Groups and Blinding

Randomization to the 3 groups will be based on an automatically generated randomization sequence (block randomization stratified by cigarette or e-cigarette use), managed through the Way to Health (WTH) Platform.

## 3.3 Study Duration, Enrollment and Number of Sites

## 3.3.1 Duration of Study Participation

The study duration per subject will be up to 12 weeks, with 1 day for screening, up to 10 weeks for the treatment phase, and 1 day for follow-up. 2 additional weeks are allotted to coordinate both initial enrollment in the quitline and remote follow-up with the adolescent.

## 3.3.2 Total Number of Study Sites/Total Number of Subjects Projected

The study will be conducted at primary care sites within CHOP's Pediatric Research Consortium (PeRC). Subjects may also be recruited through study materials distributed at up to 2 schools and posted in up to 10 other non-clinical community settings (for example, a commercial entity like convenience stores). Permission will be obtained from the school principle or non-clinical community setting building owner/proprietor before any recruitment materials are distributed.

Recruitment will stop when approximately 60 subjects are enrolled. It is expected that approximately 70 subjects will be enrolled to produce 60 evaluable subjects.

# 3.4 Study Population

### 3.4.1 Inclusion Criteria

Inclusion criteria include adolescents (aged 14-21 years), male or female, who speak English, live in Pennsylvania, screen positive for tobacco use (defined as having smoked cigarette(s) and/or used an e-cigarette on at least 1 day during the past 30 days), are interested in quitting smoking, have a smart phone, and provide consent to participate.

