### 3.4.2 Exclusion Criteria

Subjects that do not meet all of the inclusion criteria will not be enrolled.

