#### 5.1.2 Laboratory Evaluations

- Salivary cotinine measurement
  - Smoking cessation abstinence will be biologically confirmed by a salivary cotinine measurement at 10 weeks after study initiation, with a concentration of <30 ng per milliliter as a threshold.

- Subjects will use a salivary swab measurement that they are able to perform on their own that immediately reports the measurement.
- This will be performed either in front of a study team member at the primary care clinic or in front of a study team member via a video-conferencing session.
- No videos will be recorded. The specimen will be thrown away by the subject immediately after the result is noted.

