#### 6.2 Secondary Endpoints

The secondary outcome is to confirm abstinence, via salivary cotinine concentration of <30 ng per milliliter at 10 weeks after study initiation.

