- **Quit Confirmed**, defined as a salivary cotinine measurement concentration of <30 ng per milliliter.

Subject engagement with the Quitline will be reported back to the WTH platform in real time using secure, password-protected methods. This allows subjects, through their interactions with the WTH platform, to see regular progress reports of their payments. See Table 1 for payment structure.

All subjects across the 3 groups, regardless of their level of engagement with the Quitline, will be contacted by the study team at 10 weeks after study enrollment to assess their smoking status. For those reporting quitting smoking, they will be asked to complete the salivary cotinine measurement.

Table 1: Payment Structure									
	Connect to Way to Health	Quitline Enrollment	Quitline Counseling Calls			Submit Cotinine Swab*	Quit Confirmed ^		
Incentive, Quitline	\$15	\$15	\$15	\$15	\$15	\$15	\$15	\$20	\$25
Incentive, Smoking Cessation	\$15	\$15	0	0	0	0	0	\$20	\$100
No Incentive	\$15	0	0	0	0	0	0	\$20	0

\*For subjects that report quitting smoking (defined as no tobacco use in past 30 days) at the 10-week followup call. All subjects will receive \$20 for submitting the salivary cotinine swab, regardless of the result. ^Payment received for negative result, meaning cotinine level <30 ng per milliliter

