### 9.6 Informed Consent and HIPAA Authorization

Prior to the completion of any study materials, verbal or electronic informed consent from all subjects, including minors who can consent for themselves, will be obtained. Consent will be obtained over the phone or electronically, either after the clinic visit or after the REC-facilitated recruitment. Subjects will be emailed (from a CHOP study email account) an electronic version of the consent form for their records. In current clinical practice, adolescent tobacco use is screened for by pediatric practitioners at confidential adolescent visits. Parents are not present in the exam room during this part of the visit, though they may be present with the adolescent at the clinic for other portions of the visit. Thus, to project privacy of subjects, adolescent consent will be obtained after the visit, over the phone or electronically. Adolescents who screen positive for tobacco use and are interested in further treatment will be asked, by the pediatric practitioner, if they can be contacted by a member of the study team. After verbal or electronic consent is obtained, current tobacco use will be confirmed electronically or by a study team member.

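### For a subject whose only product is a nicotine-free e-cigarette, the 10-week cotinine swab cannot check the self-reported quit, and the plan does not say that such subjects are identified

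*Combined protocol and SAP*

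**What the plan says.** **Entry.** Section 3.4.1 requires that subjects "screen positive for tobacco use (defined as having smoked cigarette(s) and/or used an e-cigarette on at least 1 day during the past 30 days"; section 3.1.1 applies the same rule to clinic recruits. Section 3.4.2 adds no further bar: "Subjects that do not meet all of the inclusion criteria will not be enrolled". Entry status is established by asking: under section 9.6, "current tobacco use will be confirmed electronically or by a study team member". Outside the reference list the word nicotine does not occur. Sections 3.2 and 9.1.1 stratify randomisation by product type, so e-cigarette users are an intended group.

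**Outcome.** Section 5.1.2 states "Smoking cessation abstinence will be biologically confirmed by a salivary cotinine measurement at 10 weeks after study initiation", and no baseline cotinine is planned. Section 6.2 reads "The secondary outcome is to confirm abstinence, via salivary cotinine concentration of <30 ng per milliliter". Section 7.1 treats a quit as confirmed by the swab result alone, "defined as a salivary cotinine measurement concentration of <30 ng per milliliter".

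**Self-report comes first.** Section 3.1.3: "To be eligible for the follow-up phase, adolescents must self-report tobacco cessation". Quitting there means 30 days free of tobacco. E-cigarettes are not named in that definition, although they are named in the entry definition.

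**Payment.** In Table 1, a swab submitted after a reported quit earns $20 in every arm. A negative result adds $100 (Smoking Cessation Incentive), $25 (Quitline Incentive) or $0 (no incentive).

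**The concern.** Entry is defined by use of a device and confirmation by exposure to nicotine. The two match for cigarettes and for nicotine e-cigarettes used often enough to register. They do not match for a subject whose sole product contains no nicotine: that subject is below 30 ng/mL at randomisation and stays there regardless of behaviour. Frequency of use is a separate matter, because a daily nicotine-free vaper is just as invisible to the test.

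The swab exists to check a self-report that carries a financial reward. In these subjects it adds no information, and the reward for a negative result differs by arm. The results enter the quit-rate models of section 6.3.2, and section 6.4 intends the pilot's effect sizes to inform a larger study. With 20 per group, one false confirmed quit moves an arm's rate by 1/20 = 5 percentage points.

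**Working it through.** **The plan's own figures.** Section 6.4 gives 3 × 20 = 60 subjects. Section 3.3.2 expects about 70 enrolled for 60 evaluable, an implied loss of 10/70 = 14.3%. These are consistent and not in dispute. No planned quit rate or misreporting rate is given, so there is no further figure to reproduce.

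**Assumptions (none in the documents).**
- f: share of randomised subjects whose only product is nicotine-free.
- p: true quit rate, set to 10% in both arms for illustration.
- m: probability that a continuing nicotine-free vaper reports abstinence.
- Denominator: all 20 randomised per group, following intention-to-treat in section 6.3.2. Section 2.2 could be read as counting only those who report abstinence, which would change the percentages but not the mechanism.
- Cotinine reflects nicotine exposure. This is general pharmacology, not stated in the documents.

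**Would any such subject be enrolled?** P(at least one in 60) = 1 − (1 − f)^60.

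| f | Expected in 60 | P(at least one) |
|---|---|---|
| 0% | 0 | 0% |
| 2% | 1.2 | 70% |
| 5% | 3 | 95% |
| 10% | 6 | 99.8% |
| 20% | 12 | >99.9% |

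**Upper bound on inflation of one arm's rate.** If all such subjects keep vaping and all report abstinence, the inflation equals f: 0/20 = 0, 2/20 = 10 and 4/20 = 20 points at f = 0%, 10% and 20%.

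**Less extreme case.** Apparent rate = p + (1 − p) × f × m. Take m = 25% with no incentive and 75% in the $100 arm. At f = 10% the rates are 0.10 + 0.90 × 0.10 × 0.25 = 12.3% and 0.10 + 0.90 × 0.10 × 0.75 = 16.8%.

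| f | No incentive | $100 arm | Spurious difference |
|---|---|---|---|
| 5% | 11.1% | 13.4% | 2.3 points |
| 10% | 12.3% | 16.8% | 4.5 points |
| 20% | 14.5% | 23.5% | 9.0 points |

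**When the difference vanishes.** If m is equal in both arms and p is equal, both rates rise and the spurious difference is 0. If m is equal but p differs, the true difference is multiplied by (1 − f × m); at f = 10% and m = 25% that is 0.975, a slight dilution. If m = 0 there is no effect.

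**Why m might differ.** Follow-up payments to someone who reports quitting and tests negative are $20 + $100 = $120, $20 + $25 = $45 and $20 + $0 = $20. That is a reason to expect unequal reporting, not evidence of it.

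**The case against.** The strongest reply is that the size is wholly assumed. No section gives the share of nicotine-free-only vapers, and 0% is as compatible with the text as 20%. Entrants must want to quit, which may make such subjects uncommon. A dual user who still smokes may be caught by cotinine. All of this stands, and it is why only a range can be shown.

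Three stronger readings are tempting, and the documents do not support them.

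- A reader might infer that a negative swab alone yields a confirmed quit and its payment. It does not. Sections 3.1.3 and 7.1 require a prior report of quitting, so a continuing vaper must misreport or must not regard a nicotine-free device as tobacco. The second route is open because the follow-up definition does not name e-cigarettes. One may argue that the entry definition carries over, but the text does not say so.
- A reader might infer that nicotine content is not collected, so affected subjects can never be identified. The screening questions are mentioned in section 4.1 but not reproduced, section 5.1.1 stores a tobacco-use variable without listing its items, and Quitline enrolment takes a smoking history. The documents are silent, which is a weaker statement.
- A reader might infer that the comparison of arms is biased. A spurious difference needs misreporting that differs by arm, which is plausible given the payments but not shown.

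It is also fair to say that the missing baseline cotinine is the broader gap, since light nicotine users may also start below the cut-off. That does not remove this point. A low baseline value would not by itself distinguish the two groups, whereas a question on product content addresses this one directly.

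**Conclusion.** The point holds as a limited measurement gap. For subjects whose sole product is nicotine-free, a cotinine-confirmed quit is a self-reported quit. On an assumed share of 0% to 20%, the confirmed rate is inflated by 0 to at most 20 percentage points, the top being a worst case in which none stop and all report abstinence. Under the illustrative unequal reporting, the spurious difference between the no-incentive and $100 arms is 2.3 to 9.0 points for shares of 5% to 20%; with equal reporting and equal true rates it is zero.

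The reach is confined to the secondary cotinine-confirmed outcome. The primary outcome (section 6.1) is Quitline enrolment, use and completion, and section 7.1 defines completion by calls and self-report without cotinine. In a pilot with no formal sample-size calculation, this is a cheap improvement rather than a threat to the trial.

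**What to change.** Keep eligibility as it is. Restricting section 3.4.1 to nicotine products would remove subjects from the primary engagement outcome, which is a poor trade for this gap.

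1. Before randomisation, record product type and whether the e-cigarette used in the past 30 days contained nicotine (yes, no, don't know). If the screening form already asks this, state so in section 5.1.
2. Word the 10-week abstinence question, and the definition in sections 3.1.3 and 7.1, to cover the same products as the entry definition, naming all e-cigarettes with or without nicotine.
3. In section 6.3.2, plan to report the cotinine-confirmed quit rate with and without subjects whose only product was nicotine-free or of unknown content. The flag predates randomisation, so the restricted comparison is still between randomised groups.

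If the flag is accurate, the extra term (1 − p) × f × m drops out of the restricted analysis, and the assumed 10% true rate is recovered in each arm.

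The cost is one screening item, a wording change and one sensitivity table on a smaller set: at shares of 10% or 20%, 20 − 2 = 18 or 20 − 4 = 16 per arm, and fewer once unknowns are removed. Some adolescents will not know the nicotine content. Reporting both versions keeps the full randomised set in view.

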### 3.4.2 Exclusion Criteria

Subjects that do not meet all of the inclusion criteria will not be enrolled.

# 4 STUDY PROCEDURES

# 4.1 Screening Phase

## 4.1.1 Screening at Primary Care Visit

Adolescent cigarette or e-cigarette users may be identified at their primary care visit through standard screening approaches embedded within the electronic health record (EHR) (Epic®) at PeRC study sites. The screening procedure will also include an option to receive text messages about the study (with notice that standard text messaging charges may apply). Adolescents who screen positive for tobacco use and are interested in treatment will be approached by the study team (after the clinic visit via phone call or via text message if the individual opted in to receiving text messages about the study) to gauge interest in participating and obtain consent. Adolescents who have given permission to receive a text may be sent the following introductory message:

"Hi this is [NAME] from CHOP contacting you about a paid research study you might be eligible for. Click here to learn more: [insert REDCap link]

REDCap will be used to track attempts to contact prospective participants in an organized, secure way. The information abstracted from the EHR will be entered into REDCap. The study team will use this information to contact eligible adolescents and to document the date, time, and outcome of all contact attempts. This database will be separate from the main study database and will not be used for any purposes other than managing contact attempts.

- Primary Care Visit: Screening for Tobacco Use (using standard approaches)
- Medical Record Review
- Adolescent Consent (either electronically or over the phone)
- 4.1.2 Screening by the Study Team

Adolescent smokers may also be identified through outreach facilitated by the CHOP Research Enhancement Core (REC). REC communications will contain information about the study, an embedded link to electronic consent and screening questions, and the study team contact information (name, e-mail, phone number). This provides the option for those interested in the study to reach out to the study team directly or complete consent and study screening electronically.

Adolescents who contact the study team as a result of outreach facilitated by the REC will be screened in one of two ways:

- 1) Screening by the study team: the team will describe the study, inform prospective participants of the eligibility requirements (listed in section 3.4.1), and ask the prospective participants if they are still interested in participating. If interested, the study team will obtain verbal consent. After providing verbal consent, they will be asked to verbally answer screening questions to ascertain eligibility.
- 2) Screening electronically: the adolescents will receive an electronic consent form, which will inform the prospective participants of the eligibility requirements (listed in section 3.4.1), and ask the prospective participants if they are still interested in participating. If interested, they will provide electronic consent. After providing electronic consent, they will be asked to answer electronic screening questions to ascertain eligibility.

REDCap will also be used to track contacts by the study team with this group of adolescents. This database will be separate from the main study database and will not be used for any purpose other than managing contact attempts.

### 4.2 Study Treatment Phase

Adolescents who screen positive for tobacco use and are interested in treatment will be referred to the WTH platform. Following consent, subject information (name and mobile phone number) will be sent to WTH using secure, HIPAA- compliant methods to transmit protected health information.

- Connect to WTH Platform, randomized to 1 of 3 groups (incentive for Quitline engagement, incentive for smoking cessation, or no financial incentive)
- Enroll in smoking cessation program (the Quitline)
- Participate in the Quitline program (up to 5 coaching calls with the Quitline, every 1-2 weeks, depending upon individual subject needs)

### 4.3 Follow-up Phase

To confirm cessation, adolescents will complete a salivary cotinine specimen either collected in the clinic with a study team member or collected remotely. In the latter case, performed in front of study team member via a live-video conference.

# 4.4 Subject Completion/Withdrawal

Subjects may withdraw from the study at any time without prejudice to their care. It will be documented whether or not each subject completes the clinical study.

### 5 STUDY EVALUATIONS AND MEASUREMENTS

#### 5.1 Screening and Monitoring Evaluations and Measurements

#### 5.1.1 Medical Record Review

Adolescent smokers will be identified through standard screening approaches embedded within the electronic health record (EHR) (Epic®) at PeRC study sites or through outreach facilitated by the REC. Variables abstracted from the EHR may include the following, some of which will be used solely for contact/recruitment purposes and some of which may also be stored in the main study data base (as noted below):

- Patient name (stored in main study data base)
- Patient date of birth and age (stored in main study data base)
- Patient MRN (contact/recruitment only)
- Patient sex (stored in main study data base)
- Patient insurance status (as a proxy for Socioeconomic Status) (contact/recruitment only)
- Patient race/ethnicity (stored in main study data base)
- Patient tobacco use (stored in main study data base)
- Patient email address (stored in main study data base)
- Adolescent mobile/smart phone number (stored in main study data base)
- Parent name (contact/recruitment only)
- Parent mailing address (contact/recruitment only)
- Parent email address (contact/recruitment only)
- Parent phone number (contact/recruitment only)

If non-CHOP patients are enrolled in this study, their medical records will not be accessed. Any participant information needed for the study will be collected by directly asking the participant.

#### 5.1.2 Laboratory Evaluations

- Salivary cotinine measurement
  - Smoking cessation abstinence will be biologically confirmed by a salivary cotinine measurement at 10 weeks after study initiation, with a concentration of <30 ng per milliliter as a threshold.

- Subjects will use a salivary swab measurement that they are able to perform on their own that immediately reports the measurement.
- This will be performed either in front of a study team member at the primary care clinic or in front of a study team member via a video-conferencing session.
- No videos will be recorded. The specimen will be thrown away by the subject immediately after the result is noted.

### 5.2 Efficacy Evaluations

The main outcome of interest is adolescent smoker completion of the smoking cessation program, defined as the proportion of smokers identified in the clinic that enroll, use, and complete the Quitline program compared across the 3 groups.

The secondary outcome is to confirm abstinence, via salivary cotinine concentration of <30 ng per milliliter at 10 weeks after study initiation.

### 5.3 Safety Evaluation

This study presents no more than minimal risk to study participants, as this is a study aimed to improve adolescent cigarette or e-cigarette user engagement in a smoking cessation program. Adolescents smokers can already access the particular program – the Quitline – free-of-charge.

### **6** STATISTICAL CONSIDERATIONS

#### 6.1 Primary Endpoint

The main outcome of interest is adolescent cigarette or e-cigarette user completion of the smoking cessation program, defined as the proportion of smokers identified in the clinic that enroll, use, and complete the Quitline program compared across the 3 study arms.

#### 6.2 Secondary Endpoints

The secondary outcome is to confirm abstinence, via salivary cotinine concentration of <30 ng per milliliter at 10 weeks after study initiation.

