#### 7 STUDY INTERVENTION

#### 7.1 Description

Intervention: Subjects will be randomized within the WTH platform to 1 of 3 financial incentive groups:

- 1) Quitline Incentive: the payment structure emphasizes engaging with the quitline, with an additional smaller payment for smoking cessation. Each adolescent can receive \$15 payments for enrolling in the quitline, for maintaining involvement in the quitline program (\$15 per call for up to 5 calls), and, for those reporting abstinence, \$20 for submitting the cotinine swab and \$25 for confirmed quitting (negative cotinine swab);
- 2) Smoking Cessation Incentive: the payment structure emphasizes quitting regardless of engagement with the quitline (though the quitline will be presented as a helpful tool). Each adolescent will receive \$15 for enrolling in the quitline and, for those reporting abstinence, \$20 for submitting the cotinine swab and \$100 for confirmed quitting (negative cotinine swab); and
- 3) No financial incentive.

The WTH platform has secure financial tracking and processing systems to manage participant payments, including the ability to track earnings and pay participants via a nonintegrated payment system (ClinCard) ideally suited for adolescent subjects. ClinCards are reloadable, prepaid cards managed by Greenphire. Subjects will be able to access the payments during the study duration. Payments are based off the following:

- Enrolling in the Quitline Program, defined as the subject connecting with a Quitline counselor, providing basic information about smoking history, and discussing program details (see "Quitline Delivered Treatment" section below). To receive this payment, subjects must enroll in the Quitline within 2 weeks of start of the study;
- Maintaining involvement in the program, defined as the subject engaging in 5 proactive counseling calls with the Quitline counselors. Calls are scheduled every 1-2 weeks, depending upon the needs of the subject, and the Quitline counselor reaches out to the subject to initiate the call. Subjects eligible to receive payments for quitline calls must complete each call within a 2-week designated window;
- **Submitting the Cotinine Swab,** defined as, for those subjects who self-report quitting smoking (defined as no tobacco use in past 30 days) at the 10-week follow-up call, successfully completing the cotinine-specimen within 2 weeks of the call.

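### Payment for a negative swab differs by arm, so verification of quitting may differ too, and the plan has no analysis that separates swab return from abstinence

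*Combined protocol and SAP*

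**What the plan says.** Section 6.2 gives one quit outcome: "The secondary outcome is to confirm abstinence, via salivary cotinine concentration of <30 ng per milliliter at 10 weeks after study initiation". Section 7.1 says that all subjects "will be contacted by the study team at 10 weeks after study enrollment to assess their smoking status". Only those who report quitting are then asked for a swab, and section 7.1 defines submission as "successfully completing the cotinine-specimen within 2 weeks of the call".

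The Table 1 footnote sets a flat dollar payment of "20 for submitting the salivary cotinine swab, regardless of the result". The further payment depends on the result: "Payment received for negative result, meaning cotinine level <30 ng per milliliter". Section 7.1 and Table 1 agree that this is $100 in the Smoking Cessation arm, $25 in the Quitline arm and $0 in the third arm, "3) No financial incentive".

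Section 6.3.2 plans intention-to-treat analysis, an as-treated description, chi-square tests and a logistic model of the quit rate. It does not say whether quitting there means self-reported or confirmed, or how an unreturned swab is counted. It plans no comparison of self-reported abstinence or swab return by arm. Section 2.2, by contrast, places the comparison of confirmed quit rates among subjects who report abstinence at the call. Under Quitline Delivered Treatment in section 7.1, self-reported abstinence is also one component of completing the program.

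**The concern.** Confirmed quitting combines being abstinent with completing the verification step. The randomised payment may act on both. If honest quitters complete the swab more often where a negative result pays more, a higher confirmed rate in the Smoking Cessation arm could reflect better verification rather than more quitting.

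The plan would not reveal which. Section 6.3.2 does undertake to explore referral bonuses, which section 9.7 sets at $5 each with a cap of five ($25 in all) and which are not tied to arm. It does not examine the larger payment difference that is assigned by arm and attached to measuring the outcome.

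Section 6.4 gives the pilot's purpose as feasibility and estimating effect sizes for a larger study. An artefact of verification would pass directly into that effect size.

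**Working it through.** **Payments (section 7.1 and Table 1).** Gain to a truly abstinent subject from completing a swab that tests negative = submission payment + negative-result payment:

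- Smoking Cessation: $20 + $100 = $120
- Quitline: $20 + $25 = $45
- No incentive: $20 + $0 = $20

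The text and the table give the same figures.

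**Size of a possible artefact.** The documents state no quit rate or swab-return rate, so every rate below is an assumption. Let q be true quitting, equal in all arms, and r the return rate among quitters. Assume accurate self-report and count an unreturned swab as not quit. On all randomised subjects, confirmed rate = q × r.

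With q = 0.30 and r = 0.90, 0.75, 0.60 (Cessation, Quitline, none):

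- 0.30 × 0.90 = 27%
- 0.30 × 0.75 = 22.5%
- 0.30 × 0.60 = 18%

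Cessation minus none is 9 points, or 0.09 × 20 = 1.8 subjects per arm. The odds ratio is (0.27/0.73)/(0.18/0.82) = 1.68; for Quitline versus none it is (0.225/0.775)/(0.18/0.82) = 1.32.

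Range for Cessation versus none:

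- Smallest, q = 0.20 and return 90/80/70%: 0.20 × (0.90 − 0.70) = 4 points, odds ratio 1.35.
- Largest, q = 0.40 and return 95/70/50%: 0.40 × (0.95 − 0.50) = 18 points, odds ratio 2.45.
- Equal return, for example 80% in all arms: 0 points, odds ratio 1.00.

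**Dependence on the unsettled definition (same 30% and 90/75/60% inputs).**

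| Denominator and handling of unreturned swabs | Cessation / Quitline / none |
|---|---|
| All randomised, no swab = not quit | 27 / 22.5 / 18% |
| All randomised, self-reported quitters with no swab = quit | 30 / 30 / 30% |
| Self-reported abstainers, no swab = not quit | 90 / 75 / 60% |
| Self-reported abstainers with a swab only | 100 / 100 / 100% |

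The same data can show no difference or a 30-point one, depending on choices that the plan leaves open.

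**Consequence for inference and planning.** For 27% versus 18% at 20 per arm, exact enumeration of the uncorrected Pearson chi-square test (two-sided 0.05; section 6.3.2 does not state sidedness) rejects with probability 10.4%. With 30% in both arms and full return it rejects with probability 5.3%. Over the range above the rejection probability runs from 6.3% to 24.8%.

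If 27% versus 18% were carried forward at 80% power, with mean proportion 0.225:

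n = [1.96 × √(2 × 0.225 × 0.775) + 0.842 × √(0.27 × 0.73 + 0.18 × 0.82)]² / 0.09² ≈ 337 per arm,

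for a difference in quitting that does not exist.

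**The case against.** The strongest reply is that unequal return is conjecture. A reader might infer from Table 1 that swab return will differ by arm. The documents do not support that: they give no return rates, and several features could narrow any gap. These are the flat $20 whatever the result, the choice of clinic, home or another agreed place (section 9.2), a self-performed test with an immediate result (section 5.1.2), and a 2-week window. This objection stands, and only "may" is defensible.

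A reader might also take $120, $45 and $20 as payments for returning the swab. They are not. Returning it pays $20 in every arm, and the totals apply only to a subject who is abstinent and tests below the threshold.

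Nor is it right that self-reported abstinence is absent from the outcomes. It is part of program completion, the primary outcome, and it would form the denominator under section 2.2. But it is bundled with counselling calls in the first and not compared by arm in the second, so neither use separates verification from abstinence.

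Finally, the figures rest on assumed rates and on counting unreturned swabs as not quit, and the added false-positive risk at 20 per arm is modest in the central example. Both points are fair. The main exposure is the effect size carried forward, not the p-value.

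**Conclusion.** The concern holds as a possibility that the plan neither measures nor handles. The payment difference is certain: $120, $45 or $20 for an abstinent subject who completes verification. Its effect on swab return is unknown. If return differs as assumed (90/75/60% with 30% quitting everywhere), the spurious Cessation-versus-none difference is 9 points on all randomised subjects. It is 4 to 18 points over the wider assumptions and zero if return is equal. The conflict between the denominators in sections 2.2 and 6.3.2, and the missing rule for unreturned swabs, follow from the text and need no assumption.

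Bounding analyses might tempt a reader to credit a difference to quitting whenever its direction is the same under both extremes. That rule is unsafe because it ignores sampling error. In the null example (30% quitting in both arms, 90% versus 60% return, 20 per arm), Cessation exceeds no incentive under both extremes in 42% of trials. That is 61% of the trials in which the confirmed rate favours Cessation.

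**What to change.** In sections 6.2 and 6.3.2:

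1. Define quit as cotinine-confirmed abstinence with all randomised subjects as the denominator, and reconcile section 2.2 with this. State how self-reported quitters without a swab are counted.
2. Tabulate by arm: self-reported 30-day abstinence at the 10-week call, swab return among those reporting abstinence, and confirmed abstinence.
3. Repeat the quit contrasts with self-reported quitters who return no swab counted as all not quit and then as all quit. Report estimates with confidence intervals.
4. Interpret a confirmed-quit difference as an effect on quitting only with these results shown beside it, and adopt no direction-only rule. Carry the range, not the confirmed rate alone, into the future trial's effect size.

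The cost is one table and two model runs. Smoking status is already asked of all subjects at 10 weeks and swab submission is already tracked for payment, so no payment or procedure changes.
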